#### **5.5.4 Exploratory Efficacy Endpoints**

##### **5.5.4.1 Time to Baseline Convulsive Seizure Frequency**

Time to baseline convulsive seizure frequency is defined as the number of reported days in IVRS, from Day 1, that it takes for the cumulative number of convulsive seizures experienced to be greater than or equal to the number of seizures (per 28 days) experienced during the baseline period and will be calculated as:

Date criterion was achieved – Date of Day 1 – Number of unreported days in IVRS between Day 1 and date criterion was achieved + 1

Patients who complete the study without experiencing greater than or equal to the number of seizures (per 28 days) experienced during the baseline period, or who withdraw from the study, will be censored at the earlier of:

- Day 99.
- The date of last dose as recorded on the 'End of Treatment Study Outcome' CRF page.

The exact day used for censoring will be the day obtained from above minus the number of unreported days in IVRS between Day 1 and the day obtained from above.

Time to baseline convulsive seizure frequency will be summarized on a continuous scale, by treatment group, for patients in the ITT analysis set. The lower and upper quartiles will also be presented. The Kaplan–Meier estimates for the median time to baseline convulsive seizure frequency will be presented along with 95% CIs for the median and p-values from log-rank tests comparing each GWP42003-P group with placebo. A Kaplan–Meier plot will also be produced.

The above will be repeated using Day 15 instead of Day 1 as the start day for counting the cumulative number of convulsive seizures.

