#### **3.2 Definition of Sample Size**

A total of 186 patients will be randomized to one of 4 treatment groups (GWP42003-P 10 mg/kg/day, GWP42003-P 20 mg/kg/day, placebo 10 mg/kg/day dose volume equivalent, or placebo 20 mg/kg/day dose volume equivalent) at a 2:2:1:1 ratio. The randomization will be stratified by age group (2–5 years, 6–12 years and 13–18 years). The placebo groups will be pooled for the analyses of efficacy.

For a Wilcoxon–Mann–Whitney test comparing 2 distributions with a 2-sided significance level of 0.05, a sample size of 62 per group is required to obtain a power of at least 80%. This is based on a gamma distribution for the GWP42003-P groups with scale parameter of 65.614 and shape parameter of 1.0886, and a gamma distribution for the placebo group with scale parameter of 40.887 and shape parameter of 2.3059.

Maximum likelihood estimates using the Newton–Raphson approximation were computed for the scale and shape parameters using data from study GWEP1332 Part B.

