### 5.5.2.1 Sensitivity Analyses for the Primary Efficacy Endpoint

The following sensitivity analyses will be conducted for the primary endpoint:

- Primary endpoint analysis repeated using the PP analysis set.
- Wilcoxon rank-sum test on percentage change from baseline in convulsive seizure frequency during the treatment period. An estimate of the median differences between each GWP42003-P group and placebo, together with approximate 95% CIs, will be calculated using the Hodges–Lehmann approach.
- A rank analysis of covariance (ANCOVA) on percentage change from baseline in convulsive seizure frequency during the treatment period.

The ranks of the percentage change from baseline and the baseline convulsive seizure frequency will be calculated. The rank of the percentage change from baseline will then be analyzed using an ANCOVA model with the rank of the

baseline convulsive seizure frequency and age group (2–5 years, 6–12 years and 13–18 years) as covariates and treatment group as a fixed factor. The estimated least squares means, treatment differences, together with the 95% CIs and p-values will be presented.

- ANCOVA of log transformed convulsive seizure frequency during the treatment period.

The convulsive seizure frequency during the treatment period and the baseline convulsive seizure frequency will be log transformed prior to analysis. The log transformed convulsive seizure frequency during the treatment period will then be analyzed using an ANCOVA model with the log transformed baseline convulsive seizure frequency and age group as covariates and treatment group as a fixed factor. The back transformed estimated treatment ratios, together with the 95% CIs and p-values will be presented.

If there are any patients with no seizures during the baseline or treatment periods, then 1 will be added to the convulsive seizure frequency for all patients prior to log transformation.

- ANCOVA on percentage change from baseline in convulsive seizure frequency during the treatment period including baseline and age group as covariates and treatment group as a fixed factor. The estimated least squares means, treatment differences, together with the 95% CIs and p-values will be presented.
- Primary endpoint analysis repeated using the maintenance period (see Section 5.1.3.4) rather than the treatment period.

This analysis will include only patients who have at least 7 days of seizure data within the maintenance period.

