If the sum of the frequencies of each 14 days of the treatment period becomes less than zero, as a result of imputation, then the percentage change from baseline in convulsive seizure frequency will be set to  $-100\%$ .

The data will then be analyzed using a Wilcoxon rank-sum test.

The results of the Wilcoxon rank-sum test on the 100 imputed datasets will be combined to derive an overall p-value. The test statistic will be based on the method provided by Rubin and a modified macro from Mogg.

For each analysis, the increment in the positive value of  $k$  will stop once the overall p-value is greater than 0.05. The decrease in the negative values of  $k$  will continue until the overall p-value becomes smaller than the p-value from the primary efficacy analysis, for the corresponding Dose Level.

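### The exploratory log-rank tests and the MNAR Wilcoxon test leave out the age strata used in randomization, which makes them conservative if age is related to outcome

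*SAP*

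**What the plan says.** SAP 3.2 and Protocol 7.2 and 13.1 set the design: "The randomization will be stratified by age group", with bands of 2–5, 6–12 and 13–18 years.

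Age group then appears in:
- the primary negative binomial model (SAP 5.5.2);
- the rank, log-transformed and percentage-change ANCOVAs (5.5.2.1);
- the CMH responder tests (5.5.3.1.2 and 5.5.3.2.1);
- the CGICSD model (5.5.3.2.5);
- the sleep, sleepiness, QOLCE and Vineland-II ANCOVAs (5.5.3.2.7 to 5.5.3.2.10);
- the other exploratory endpoint, seizure-free days (5.5.4.2).

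It does not appear in SAP 5.5.4.1, which gives Kaplan–Meier medians and "p-values from log-rank tests comparing each GWP42003-P group with placebo". Nor does it appear in SAP 5.5.2.1.1, where, once values are imputed, "The data will then be analyzed using a Wilcoxon rank-sum test". That section imputes from baseline and earlier 14-day frequencies, pools 100 imputed results through a modified macro, and sweeps a sensitivity parameter k. Positive k rises until the pooled p-value exceeds 0.05. Negative k falls until the pooled p-value drops below the primary analysis p-value for that dose. No reason is given for leaving age out of either analysis.

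**The concern.** When allocation is balanced within strata and the strata differ in outcome, an unstratified test keeps the between-stratum spread in its null variance, although that spread cannot contribute to the treatment difference. The variance is too large and the test rejects too rarely.

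For the log-rank tests this means some lost power on an exploratory endpoint.

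For the MNAR analysis the effect is on interpretation. The p-value is the stopping rule for k. A conservative test crosses 0.05 at a smaller penalty, so the reported tipping point would partly reflect an omitted design factor and not only the missing data. The other end of the sweep is judged against a p-value from a model that does adjust for age.

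**Working it through.** **The plan's own figure.** SAP 3.2 bases the sample size on an unstratified Wilcoxon–Mann–Whitney test: "2-sided significance level of 0.05, a sample size of 62 per group is required to obtain a power of at least 80" percent. Its inputs are two gamma distributions: active, scale 65.614, shape 1.0886; placebo, scale 40.887, shape 2.3059.

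- Numerical integration gives P(active < placebo) = 0.643.
- Noether's formula: total N = (1.960 + 0.842)² / [12 × 0.25 × (0.6432 − 0.5)²] = 127.5, or 63.8 per group.
- Power at 62 per group: Φ(√(12 × 0.25 × 124) × 0.1432 − 1.960) = Φ(0.803) = 0.789.
- With the exact variance under the alternative, power is 0.796. Simulation (40,000 runs) gives 0.793.

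The stated 80% therefore reproduces to within about one point for the unstratified test.

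**What stratifying changes.** The documents give no age effect, stratum sizes or event times, so the following are assumptions:
- 62 v 62 patients, with 18, 26 and 18 per arm in the three age strata.
- The outcome (for the log-rank, the event rate) is multiplied by exp(−d), 1 and exp(+d) across strata. The ratio between the outer strata is exp(2d): 1.65 at d = 0.25, 2.72 at d = 0.5 and 7.39 at d = 1.0.
- Wilcoxon: the gamma distributions above, 20,000 runs.
- Log-rank: exponential times, placebo median 35 days, hazard ratio 0.6, censoring at Day 99, 6,000 runs.

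The van Elteren statistic is Σ[(Wₛ − Eₛ)/(Nₛ + 1)] / √Σ[Vₛ/(Nₛ + 1)²], with Vₛ = mₛnₛ(Nₛ + 1)/12. The stratified log-rank sums observed minus expected events, and their variances, over strata. Each cell shows unstratified v stratified.

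| d | Wilcoxon type I error | Wilcoxon power | Log-rank type I error | Log-rank power |
|---|---|---|---|---|
| 0 | 0.048 v 0.050 | 0.796 v 0.791 | 0.055 v 0.054 | 0.710 v 0.699 |
| 0.25 | 0.041 v 0.049 | 0.785 v 0.787 | 0.047 v 0.051 | 0.682 v 0.693 |
| 0.5 | 0.026 v 0.052 | 0.759 v 0.788 | 0.040 v 0.053 | 0.638 v 0.683 |
| 1.0 | 0.004 v 0.049 | 0.631 v 0.793 | 0.019 v 0.054 | 0.458 v 0.670 |

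From the unrounded results, the power change from stratifying, in points (Wilcoxon, log-rank), is:
- d = 0: −0.6, −1.2
- d = 0.25: +0.2, +1.0
- d = 0.5: +3.0, +4.5
- d = 1.0: +16.3, +21.2

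The Monte Carlo standard error of a single power estimate is about √(0.8 × 0.2/20,000) = 0.3 points for the Wilcoxon and √(0.7 × 0.3/6,000) = 0.6 points for the log-rank. The differences at d = 0 and d = 0.25 are therefore small and imprecise.

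**Reading this for the tipping point.** At d = 0.5 the unstratified test gives p < 0.05 only 2.6% of the time under the null, so stopping at p > 0.05 behaves like stopping at about 0.026 on a calibrated scale. At d = 0.25 the corresponding level is about 0.041. On average, the sweep stops at a smaller k than a calibrated test would allow. These runs use complete data. The shift in k after multiple imputation was not simulated.

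**The case against.** Several points on the other side are sound.

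- **The plain Wilcoxon test is covered.** SAP 5.5.2.1 also plans a "Wilcoxon rank-sum test on percentage change from baseline in convulsive seizure frequency during the treatment period" without imputation and without age. A reader might infer that this is equally at fault. The documents do not support that: the same list contains a rank ANCOVA on the same outcome with age group and ranked baseline, and the unstratified test is the one used for the sample size. It can stay.
- **There is no validity problem.** A reader might infer that ignoring the strata endangers the trial's conclusions. The error is toward conservatism, the primary model includes age, and none of these tests is in Table 3.
- **The log-rank test is not a check on the primary model.** It belongs to a separate exploratory endpoint, so a mismatch with the primary analysis is not an argument there. The argument is power and consistency with SAP 5.5.4.2.
- **The age effect may be small.** Protocol 3.1 says convulsive seizures become less frequent after age five, which might suggest a strong effect. But both outcomes are relative to the patient's own baseline, which removes age differences in seizure level and leaves only age differences in change. The large gains at d = 1.0 need a 7.4-fold ratio between the outer strata.
- **Stratifying is not free.** With no age effect it loses a little power.
- **The protocol specifies the MNAR Wilcoxon the same way** (Section 13.6.2.1), so the SAP does not conflict with it.

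These points narrow the concern to two analyses at low severity. They do not remove it: the MNAR analysis has no age-adjusted version, and no reason is given for leaving age out.

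**Conclusion.** The point holds in limited form. The log-rank tests in SAP 5.5.4.1 and the MNAR Wilcoxon in SAP 5.5.2.1.1 omit the randomization strata, out of line with almost all the other efficacy tests. If age is related to outcome, they are conservative, and the MNAR tipping point tends to be reached too early.

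The size rests wholly on assumed age effects, stratum sizes and, for the log-rank, event times. Within those assumptions the gain is about 0 to 1 power point for a small effect and 3 to 4.5 points for a moderate one, against a loss of about 0.5 to 1 point if there is no effect. Severity is low.

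One related omission lies outside this point but should be looked at together with it. The CGIC proportional odds model (SAP 5.5.3.1.3) names only treatment group, whereas the CGICSD model includes age group, and CGIC is in Table 3 as tests 7 and 8.

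**What to change.** Before unblinding:

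1. In SAP 5.5.4.1, stratify the log-rank tests by the age group used at randomization, for both the Day 1 and Day 15 versions. This is a strata specification in the existing procedure.
2. In SAP 5.5.2.1.1, replace the rank-sum test with the van Elteren test on each imputed dataset, and adapt the macro that pools the 100 results so that it takes the stratified statistic and its variance. Consider adding age group to the imputation models too, so that imputation and analysis agree.
3. Leave the plain Wilcoxon test and its Hodges–Lehmann interval as they are, and name the rank ANCOVA as its age-adjusted companion.
4. Record the MNAR change in SAP 5.8, because the protocol describes an unstratified test.

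No extra data are needed. The cost is minor programming and validation, mainly of the pooling macro, plus the small power loss if age has no effect. If the sponsor prefers the unstratified tests, one sentence giving the reason would be enough.

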#### **5.5.4.2 Number of Convulsive Seizure Free Days**

The number of convulsive seizure free days during each period will be based on 28-day averages and calculated as:

$$\left( \frac{\text{Number of seizure free days in the period}}{\text{Number of reported days in IVRS in the period}} \right) \times 28$$

The change from baseline in convulsive seizure free days per 28 days will be analyzed for the treatment period using an ANCOVA approach. The model will include baseline and age group as covariates and treatment group as fixed factor.

The estimated least squares means, treatment difference, together with the 95% CIs and p-value will be presented.

The analysis will be repeated for the maintenance period. Analysis on the maintenance period will include only patients who have at least 7 days of seizure data within the maintenance period.

#### **5.5.5 Subgroup Analyses**

To assess the degree of effect heterogeneity, effect modifier analyses are proposed, on the ITT analysis set, for the primary efficacy endpoint and the key secondary efficacy endpoint of  $\geq 50\%$  reduction in convulsive seizure frequency.

For the primary efficacy endpoint, the effect modifier analysis will be performed using the negative binomial regression analysis as described in Section 5.5.2. The model will be updated to include covariates for each level of the effect being tested (excluding a reference level), individually and with interactions with time, interactions with treatment arm and interactions with time and treatment. A separate model will be used for testing each effect. The treatment ratios (GWP42003-P vs. placebo), percent reduction and 95% confidence intervals will be presented for each level of the effect. In addition, the effect by time by treatment arm interaction p-value, testing the hypothesis that the effect level treatment ratios are homogeneous, will be presented.

For the key secondary efficacy endpoint of  $\geq 50\%$  reduction in convulsive seizure frequency, patients with a  $\geq 50\%$  reduction in seizure frequency will be modelled using logistic regression, including stratified age group and treatment arm as covariates. The model will also include covariates for each level of the effect being tested (excluding a reference level), individually and with interactions with treatment arm. A separate model will be used for

testing each effect. The number and percent of responders, and odds ratios and 95% confidence intervals will be presented for each level of the effect. In addition, the effect by treatment arm interaction p-value, testing the hypothesis that the effect level odds ratios are homogeneous, will be presented.

The following effects will be tested:

- Age group (2-5 years, 6-12 years and 13-18 years). Note: stratified age group will be removed as a covariate for this model.
- Sex (Male, Female).
- Region (US, Rest of the World).
- Clobazam use (Yes, No).
- Valproic acid use (Yes, No).
- Stiripentol use (Yes, No).
- Clobazam use and Stiripentol use (Yes/Yes, Yes/No, No/Yes, No/No).
- Levetiracetam use (Yes, No).
- Topiramate use (Yes, No).
- Baseline average convulsive seizure frequency per 28 days ( $\leq$  observed Tertile 1,  $>$  observed Tertile 1 to  $\leq$  observed Tertile 2,  $>$  observed Tertile 2). The observed tertile values will be rounded to the nearest whole number.
- Number of concurrent AEDs ( $<3$ ,  $\geq 3$ ).
- Number of prior AEDs ( $<4$ ,  $\geq 4$ ).
- Number of prior and concurrent AEDs ( $<8$ ,  $\geq 8$ ).

## 5.6 Safety Evaluation

### 5.6.1 Exposure to IMP

Patients are required to take IMP twice daily (morning and evening). The first dose will be taken in the clinic on Day 1. The date of final dose in the treatment phase will be recorded on the CRF. The date of final dose, for patients who enter the taper period, will be recorded on the CRF at the end of taper visit.

The total number of dosing days in the treatment phase will be calculated as:

$$(\text{Date of last dose in the treatment phase} - \text{Date of Day 1}) + 1$$

The date of last dose in the treatment phase will be obtained from the CRF at the end of treatment visit.

Any missed doses during treatment should be recorded on the 'IMP Missed Doses Log' CRF page. The number of days with any missed doses and the number of days where IMP was not taken in the AM nor PM will be summarized based on data in the treatment phase (Day 1 to end of treatment visit).

In addition, the number of days in which IMP was taken at least once (AM or PM) will be summarized and calculated as:

$$\text{Total number of dosing days} - \text{the number of days where IMP was not taken in the AM nor PM}$$

The number of days in which IMP was taken both AM and PM will be summarized and calculated as:

Total number of dosing days – the number of days with any missed doses

The above summaries will be presented for all patients and repeated for patients who completed the treatment phase.

In addition, the expected daily volume of IMP to be administered during the treatment phase, once a patient has titrated to target dose, will be summarized by treatment.

The expected daily volume of IMP will be calculated as:

$$2 \times [\text{Weight (kg) at Day 1} \div 10 \text{ and rounded to the nearest 0.1}]$$

for patients randomized to the 20 mg/kg/day dose level and:

$$2 \times [\text{Weight (kg) at Day 1} \div 20 \text{ and rounded to the nearest 0.1}]$$

for patients randomized to the 10 mg/kg/day dose level.

Finally, IMP compliance will be summarized by treatment and calculated as:

$$100 \times (\text{Number of days IMP taken at least once} + \text{number of days IMP taken both AM and PM}) \div (2 \times \text{day of completion or withdrawal during the treatment period})$$

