#### 8.1.2 Dose Escalation, Dose Adjustments and Down-Titration

The titration regimen is shown in [APPENDIX 4](#). All patients will be weighed during Visit 2 and the daily volumes of IMP solution to be taken during the two-week titration period and for the remainder of the maintenance period will be calculated via the IVRS and the dosing regimen provided to the patient and/or caregiver. Patients should achieve their target Dose Level before the end of the two-week titration period; however, the titration period will be considered two weeks long to ensure all patients have achieved stable dosing from Visit 3 onwards (maintenance period). Further information on dispensing procedures will be provided in a separate Pharmacy Manual.

Each patient will take their first dose of IMP at Visit 2 (Day 1) and their final maintenance dose of IMP at Visit 8 (Day 99). If an unacceptable AE develops at any time during the titration period, dosing should initially be suspended or amended, at the investigator's discretion, until the event has resolved or is well tolerated. During the maintenance period, patients should continue on a stable dosing regimen at the target Dose Level. If that dose becomes poorly tolerated, the investigator may consider temporarily or permanently reducing the dosage for the remainder of the maintenance period. However, where possible, the patient should be encouraged to return to the target Dose Level.

Patients who do not immediately enter the OLE study at Visit 8 will have their dose of IMP tapered gradually (10% each day) over a period of 10 days. However, the taper period may be interrupted if the patient wishes to enter the OLE study within seven days of Visit 8. Patients who withdraw early should also begin the taper period following the Withdrawal visit (unless continued dosing is not possible due to an AE). Patients participating in the taper period will return used and unused IMP to the clinic at Visit 9 ('End of Taper Period' visit).

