### 5.1.3.3 Treatment Period

The treatment period is defined as Day 1 to the earlier of:

- Day 99.
- The date of last dose as recorded on the 'End of Treatment Study Outcome' CRF page.

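### SAP 5.6.1 subtracts missed-dose days counted to the end-of-treatment visit from dosing days that stop at the last dose, so days dosed and compliance can be understated when the last dose comes first

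*SAP*

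**What the plan says.** SAP 5.6.1 defines total dosing days as the last treatment-phase dose date minus the Day 1 date, plus one. For the end date it says: "The date of last dose in the treatment phase will be obtained from the CRF at the end of treatment visit".

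Missed doses come from a log: "Any missed doses during treatment should be recorded on the 'IMP Missed Doses Log' CRF page". Two counts are taken from it, days with at least one dose missed and days with both missed. These counts "will be summarized based on data in the treatment phase (Day 1 to end of treatment visit".

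Days with both doses taken are then "Total number of dosing days – the number of days with any missed doses". Days with at least one dose taken are total dosing days less "the number of days where IMP was not taken in the AM nor PM". Compliance is 100 times the sum of these two results, divided by twice the "day of completion or withdrawal during the treatment period".

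Two other places bear on the dates. SAP 5.1.3.3 ends the treatment period at the earlier of Day 99 and "The date of last dose as recorded on the 'End of Treatment Study Outcome' CRF page". Protocol 8.1.2 foresees that dosing may already have ended when a patient withdraws: "Patients who withdraw early should also begin the taper period following the Withdrawal visit (unless continued dosing is not possible due to an AE". Protocol 9.2.8 brings Visit 8 forward for withdrawers, so their end-of-treatment visit is the Withdrawal visit.

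**The concern.** The formula subtracts a count made over one window from a count made over another. Total dosing days close at the last dose, and the missed-day counts close at the visit. Nothing in SAP 5.6.1 limits missed days to those on or before the last dose. Read literally, each day between the last dose and the visit is a day without drug inside the missed-day window, so it is subtracted from a total that had already left it out.

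At stake are the days-taken summaries and the compliance percentage: Table 7.1 (treatment compliance), Table 10.1 (exposure) and Listing 10.1 in SAP Appendix 5. No efficacy analysis and no hypothesis test uses them.

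**Working it through.** The plan states no compliance figure, so there is nothing to reproduce. The check applies the SAP 5.6.1 formula to worked cases.

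**Inputs**
- T = total dosing days, which equals the day number of the last treatment-phase dose (SAP 5.6.1).
- N = days with neither dose taken; A = days with any dose missed (SAP 5.6.1, from the log).
- D = day of completion or withdrawal (SAP 5.6.1). The section does not say whether this is the visit day or the last-dose day, so both are shown.
- g = visit day minus last-dose day. The documents do not give it; the gaps below are assumptions.

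**Formula**

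Compliance = 100 × [(T − N) + (T − A)] / (2 × D)

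**Sanity check, no gap.** Last dose and visit both on Day 99:
- No misses: 100 × (99 + 99)/198 = 100.0%.
- Two days fully missed and five half missed, so N = 2 and A = 7: 100 × (97 + 92)/198 = 95.5%, as it should be.

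The formula is therefore right when the two dates coincide.

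**With a gap.** If all g days after stopping enter the log, N and A each rise by g. Days taken at least once and days with both doses taken each fall by g. Compliance falls by 100 × 2g/(2D) = 100 × g/D points. If only some of those days are logged, the fall is proportionately smaller.

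**Worked case.** Last dose Day 40, visit Day 47, no misses while on drug, Days 41 to 47 logged as missed (g = 7):
- Days taken: 40 − 7 = 33, against 40 with matched windows.
- D = 47: 100 × (33 + 33)/94 = 70.2%, against 100 × 80/94 = 85.1%. The shortfall is 100 × 7/47 = 14.9 points.
- D = 40: 100 × 66/80 = 82.5%, against 100 × 80/80 = 100%. The shortfall is 100 × 7/40 = 17.5 points.

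**Range over assumed gaps** (no misses while on drug, all gap days logged; each cell is the literal result, then the result with matched windows):

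| Last dose / visit day | g | D = visit day | D = last-dose day |
|---|---|---|---|
| 28 / 29 | 1 | 93.1% vs 96.6% | 96.4% vs 100% |
| 60 / 67 | 7 | 79.1% vs 89.6% | 88.3% vs 100% |
| 90 / 99 | 9 | 81.8% vs 90.9% | 90.0% vs 100% |
| 40 / 50 | 10 | 60.0% vs 80.0% | 75.0% vs 100% |
| 5 / 15 | 10 | −33.3% vs 33.3% | −100% vs 100% |

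The last row is impossible as a compliance figure. It arises whenever g exceeds T.

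**The case against.** The strongest reply is that the error needs days after stopping to be logged as missed doses. The log is for doses missed during treatment, and once drug has been stopped for good no dose is due. On that reading nothing is wrongly subtracted. This stands as a real limit, because the CRF completion rules are not in the documents. It does not settle the matter: SAP 5.6.1 leaves the phrase undefined, and SAP 5.1.2 uses the same log to find the first-dose date when that dose was not given on site. The log is therefore not confined by design to the span from first to last dose.

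A second reply is that the stated window was probably meant to keep taper-period misses out. That is plausible, but the window as written still runs past the last dose for some patients.

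A third concerns the denominator. A reader might infer that days after stopping are deducted twice, once in the numerator and again by lengthening the denominator. That requires D to be the visit day. SAP 5.6.1 places D within the treatment period, and SAP 5.1.3.3 ends that period no later than the last dose. Together they favor the last-dose day, and then the days are deducted once, still wrongly. The documents do not support treating double deduction as settled.

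Fourth, the group is narrow. By default withdrawers taper after the Withdrawal visit (Protocol 8.1.2), and the final maintenance dose is taken in clinic at Visit 8 (Protocol 9.2.8). Where tapering starts at the decision to stop (Protocol Section 10), drug is still being taken. This stands. It also stands that the per-patient listing would expose implausible values, and that discontinuations for adverse events have their own tables (12.3 and 12.4).

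**Conclusion.** The mismatch of windows in SAP 5.6.1 is real, and no other section aligns the two counts. Days taken can be understated by up to g, and compliance by up to 100 × g/D points, under either reading of D. Total dosing days itself is unaffected.

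The result rests on two conditions: the last treatment-phase dose precedes the end-of-treatment visit, and at least some of the days between enter the missed-dose count. If either fails, the error is zero. The documents give neither the number of such patients nor the gap lengths, so the effect on any group summary cannot be sized.

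A reader might infer that compliance is understated in early stoppers as a matter of course, or that the active arms would look less adherent because patients stop for adverse events. The documents support neither. The first depends on logging practice. The second needs stopping rates and reasons by arm, and Protocol 8.1.2 mentions an adverse event only as an exception to tapering. This is a minor correction to descriptive outputs; the primary analysis and type I error control are untouched.

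**What to change.** In SAP 5.6.1, for the days-taken and compliance calculations, count missed-dose days only from Day 1 to the date of the last treatment-phase dose, the window already used for total dosing days. If the separate summary of missed-dose days is to keep running to the visit, label it so and do not feed it into the subtraction.

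Also state whether the day in the denominator is the last-dose day, which is what SAP 5.1.3.3 implies for a patient who stops before Day 99, or the visit day. Either can be defended, but they answer different questions. With matched windows and no misses on drug, a patient with last dose on Day 40 and visit on Day 47 scores 100% on the first and 85.1% on the second. With the last-dose day, early stopping shows in exposure duration and not in the compliance percentage.

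The cost is a sentence or two in the SAP and a date filter in the compliance program. No new data are needed.
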